6.1 Description of randomisation and code breaking

6.1.1 Randomisation

Randomisation will be carried out intraoperatively once debridement of the chondral / osteochondral lesion has been performed and the true size of the defect can be measured. Once the size of the lesion has been confirmed to be no more than 4cm^2 , and therefore eligible for inclusion (see Section 5.5), randomisation will be performed. Consent and baseline assessment will be completed prior to surgery. Randomisation will be performed by a member of the local team not involved in data collection or participant follow-up using a secure internet-based randomisation system ensuring allocation concealment. The randomisation system will be available as part of the bespoke study database. Randomisation will be carried out by a member of the research team using their personal login details. Participants will be allocated in a 1:1 ratio to either microfracture plus microstructural scaffold (AMIC) or microfracture alone. The randomisation scheme will take into account important prognostic factors.

Any barriers to successfully randomising once debridement of the chondral/osteochondral lesion has been performed will be explored in phase 1 (internal pilot) of the RCT. Prospective surgeons have confirmed that there are not any foreseen issues around availability of instruments or materials with the above strategy.

6.1.2 Manual randomisation

Instructions on how to perform a manual randomisation will be provided to the research team should the online randomisation system fail.

6.2 Blinding

Randomisation will be performed by a member of the local team (e.g. unblinded research staff, theatre staff, surgical team or the operating surgeon) using an online system, after the size of the lesion has been confirmed to be no more than 4cm² and other inclusion/ exclusion criteria are satisfied hence the patient is eligible for inclusion. Anyone involved in the surgery who knows the patient's allocation will be asked not to discuss which operation the participant received. Research nurses responsible for data collection and participant follow-up will not randomise patients and will not be in the operating theatre.

Participants, their clinical care team (except for staff directly involved in the surgery) and research nurse(s) responsible for participant follow-up will not be informed of the allocation until the end of the study. This could be until at least 10 years post-randomisation pending further funding for follow up. If the patient is aware of their allocation before their follow up is finished, it is possible that knowing which treatment they received may influence their decision making regarding further treatment. The time period for blinding will be explained to patients in the PIL. The PIL clearly explains that it is not known which procedure is better. Therefore, in the event of inadvertent unblinding of a participant, it is unlikely that he or she would have a strong expectation that one or other method would lead to a more favourable result, but we would like to avoid taking this risk.

Microfracture and microfracture plus scaffold insertion (AMIC) can both be performed either arthroscopically or through an arthrotomy, these different approaches have different incision sizes. Arthrotomy is more likely to be performed in the scaffold group but we will ask the clinical care team to avoid defining that in the consent process. Patients will be consented for either approach as required. Therefore, we do not expect participants to be unblinded due to the scar size. The rehabilitation and other aspects of clinical care will be the same for both groups, so would not create unblinding. We will assess the success of blinding by asking the patient and all outcome assessors which treatment they think was received (Bang blinding index). Blinding of participants and study personnel will minimise performance bias.

We will provide sites with a study operation note template, which can be used to record the operation and details of the operation that are not blinded. The note will therefore not contain details about the study intervention. A copy of this can be kept in the medical notes, along with details of how to unblind, and another copy can be kept in the patient's CRF folder. The use of the operation note will be optional.

An unblinded CRF form will capture any details of the operation which could unblind staff members. This will be entered into the study database by an authorised unblinded member of staff and then placed in a sealed envelope. This will be stored in the study site file.

6.2.1 Unblinding

We do not anticipate unblinding will be requested on clinical grounds, e.g. to treat a complication. The intervention and control are similar surgical procedures with common risks, side effects and complications that occur at similar rates. The allocation of a patient to either arm of the study would not affect the management of the patient if a complication (e.g. infection or bleeding) were to occur meaning that the treating clinicians would not need to be aware of the allocation in order to deliver effective and appropriate treatment. However, for the rare occasion where unblinding is required, the unblinded CRF described in section 6.2 can be removed from the sealed envelope within the site file. Any member of staff accessing the documents in the sealed envelope will have to record the reason for accessing the documentation. This will provide a record of the staff who have been unblinded and the reason. Unblinding rates will be monitored throughout the trial by the study team and by the independent Data Monitoring and Safety Committee (DMSC) that will be established to oversee participant safety in the trial. Participants will be made aware before entering the study that they will not be told which treatment they will receive until the end of the trial.

6.3 Research procedures

6.3.1 Patient reported outcomes

Baseline comorbidity, KOOS, IKDC, HRQoL, Tegner-Lysholm activity grading scale and the WPAI questionnaires will be administered prior to randomisation. If the comorbidity questionnaire is not completed by the patient, this information should be sourced from the patients medical notes.

Questionnaires to capture clinical outcomes, HRQoL and resource use will be administered at approximately 3 months, 6 months, 1 year and 2 years when the participant attends the site for a clinical follow-up (up to 1 year) or research follow up (2 years), with alternative arrangements for participants who do not attend (e.g. postal, telephone or on-line data collection). If the patient does not complete the questionnaire at the site or if the questionnaire is not returned on time, then the site should follow this up with a phone call to the patient to ensure the questionnaire is returned. The completion rates of the questionnaires will be monitored via the study database and flagged to sites if missing.

6.3.2 Treatment adherence

Withdrawals during surgery should not occur due to the nature of the treatment; the duration of the intervention is the time taken to insert the scaffold. Problems with adherence (e.g. giving rise to cross-overs) are also expected to be low given randomisation will take place after debridement and confirmation that the lesion size is eligible. Operative details will be collected for all participants to allow adherence to be monitored.

6.3.3 Rehabilitation procedure – all participants

The rehabilitation protocol will be for all participants to mobilise protected weight bearing with crutches for 6 weeks post operatively and to use a brace limiting range of motion to 0-90 degrees flexion for 6 weeks. For patella and trochlea lesions there will be additional restriction of 0-30 degrees flexion for the first 2 weeks. Increased restriction will be at the discretion of the surgeon depending on lesion site, size and associated injuries.

6.4 Duration of treatment period

The duration of the treatment commences when the patient enters the operating room and concludes when the patient leaves the operating room after their surgery. The duration of the procedure will be between 30 minutes and 1 hour 30 minutes for both procedures. (experimental group 20 mins longer).

6.5 Definition of end of trial

Active data collection will continue up until 2 years post-randomisation. The patient's active involvement in the trial will end at this point. However, if we receive further funding we may continue follow up for at least 10 years. Data collection for the whole trial will be complete when the final randomised participant has completed the 2 year post randomisation. assessments. The end of the trial will be when the database is closed, all the data queries have been answered. This will allow time to process an amendment to continue with further follow up should further funding be awarded.

6.6 Data collection

Each patient will be assigned a unique study number. All data recorded on paper relating to the participant will be located in Case Report Form (CRF) folders, which will be stored securely at individual sites. Staff with authorisation to make changes to the study records, including the study database, will be listed on the study delegation log maintained at each specialty/centre. The baseline data will be collected after consent. Consenting patients will be seen by an authorised member of the local research team (as specified in the delegation log) who will answer any questions, confirm the patient's eligibility and take written informed consent if the patient decides to participate.

Patients who choose to consent using electronic consent methods will provide their email address to the local research team to receive a link to the electronic consent form.

Data collection will include the following elements:

- (a) A screening log of all patients identified with a symptomatic chondral lesion will be invited to participate;
- (b) Patients approached and assessed against the eligibility criteria and, if ineligible, reasons for ineligibility;
- (c) Consent information collected prior to randomisation in all participating patients;
- (d) Baseline information (e.g. sociodemographcs, history, planned operation and response to health, comorbidities and work status questionnaires) collected in all participating patients;
- (e) Data relating to the participant's surgery and hospital stay collected in all participating patients;

- (g) Data on health status, activity, knee function, productivity (collected via questionnaires), adverse events and resource use collected at 3, 6, 12 and 24 months post-randomisation for all participating patients.
- (h) Bang Blinding Index from researchers and patients at 3 and 24 months

In the event that unforeseen circumstances prevent sites from being able to carry out their normal activities, they should contact the BTC who will do everything they can to help. This may include, but is not limited to, sending out questionnaires and reminders on their behalf.

To minimise bias, outcome measures are defined as far as possible on the basis of objective criteria and all personnel carrying out outcome assessment will be blinded.

Table 1 Data collection

Data item	Baseline	Intra- operatively	Discharge	Post-randomisation					
				3	6	12	24	5	10
				months	months	months	months	years*	years*
Demography	✓								
Relevant medical history	✓								
Comorbidities	~								
Operative details		V							
Bang blinding index				~			~		
KOOS	~			✓	✓	✓	✓	✓	✓
IKDC	~			✓	✓	✓	✓	✓	✓
Activity grading	~			✓	✓	✓	✓	✓	✓
Productivity	√			✓	✓	✓	✓	✓	✓
HRQoL (EQ-5D)	√			✓	✓	✓	✓	✓	✓
Post-operative complications			~	~	~	~	~	~	✓
Rehabilitation			V	✓					
SAEs, including re-admissions [¥]			V	~	✓	✓	✓	~	✓
Resource use		√		✓	✓	✓	✓	✓	✓

^{*} not costed as part of this study; events would be captured through routine data (HES)

To minimise bias, outcome measures are defined as far as possible on the basis of objective criteria. All personnel carrying out outcome assessment will be blinded; this will minimise detection bias.

^{*} SAEs will be subject to expedited reporting to the Sponsor up to 3 months post-randomisation. SAEs collected for later time points will not be subject to expedited reporting.

6.7 Source data

The primary data source will be the participant's medical records, alongside the data collection forms for the study. The completed patient questionnaires will be the primary data source for information on the patients' health, knee function, productivity, comorbidities and activity.

6.8 Planned recruitment rate

6.8.1 Phase 1

Phase 1 recruitment will take place in up to 8 sites for 8 months. There will be a review of the progression criteria at the end phase 1. See section 7.4.

6.8.2 Phase 2

If the progression criteria are met, recruitment into Phase 2 will continue in an additional approximately 8 sites (at least 16 sites total). All participants will be followed up for 24 months.

6.9 Participant recruitment

All patients identified with a symptomatic chondral or osteochondral lesion will be invited to participate. Potential trial participants will be identified by clinical teams. Prior to screening, patients will be seen in specialist knee clinics or in consultation with a specialist knee surgeon, for example an orthopaedic elective knee clinic or acute knee clinic which patients are referred to from triage services (e.g. fracture clinic, GP or physiotherapy). During the clinic appointment the clinician will review the patient's MRI scan, if available, and once the patient is confirmed as requiring treatment for a symptomatic defect, they will be listed for surgery and could be on a waiting list for up to 9 months (waiting times will vary between centres). Patients may be informed of the study at the clinic, but due to long waiting times, it is anticipated that patients may be identified from surgery waiting lists and approached closer to their surgery date, for example at a pre-operative assessment clinic or consent clinic.

There will be a three-stage screening process. The initial stage of screening will take place once the patient is identified on the surgery waiting list or from a clinic virtual or face to face consultation. This will involve assessment of eligibility criteria, including preoperative imaging where the lesion size must be anticipated to be less than 4cm^2 for the patient to be eligible. If none of the exclusion criteria have been met, the patient will be approached and given a PIL at this stage, either in person at a clinic or they will be sent the PIL in the post or via email by a member from the research team. If patients are sent a PIL in the post or via email, a member of the research team may have a telephone consultation or video call to explain the study and answer any questions (see 6.9.1 for further information). The PIL will include contact details for the research team in case the patient has any questions.

Following this, at 2 to 8 weeks before surgery the patient will attend a pre-operative assessment or other clinic (this will vary across sites). The surgeon will confirm the patient's preoperative eligibility and a member of the research team will gain consent (if the patient decides to participate). All individuals taking informed consent will be GCP trained. During the consultation potential participants will be fully apprised of the potential risks, benefits and burdens of the study. They will also be informed that if the lesion size is determined to be too big, they will not

be eligible for the study and will receive standard care. If a site is not able to take consent at a preoperative clinic, providing the patient has had time to consider the study and ask any questions, written consent can be taken on the day of surgery by a member of the research team. The patient will keep a copy of the consent form, the research team will file another copy in the patient CRF folder and a final copy will be stored in the patient's medical records. Details of all patients approached for the trial and reason(s) for non-participation (e.g. reason for being ineligible or patient refusal) will be documented.

The final stage of screening will occur in theatre when the patient's lesion size can be accurately measured following debridement of all loose and unstable cartilage to define the true lesion size, and eligibility can be fully confirmed. The patient will therefore be randomised in theatre.

6.9.1 Study information pack and consent provision

All potential patients will receive an invitation letter and PIL, approved by the HRA/NHS REC, describing the study as part of a study information pack. These documents may be given to the potential patient in person or sent via post or via email. The study information pack, if sent by post or email may also include the SISMIC patient consent form and baseline questionnaire for completion before surgery if the patient consents to join the trial. Whether the questionnaire is sent and completed before attending the hospital for surgery or is completed when the patient attends the hospital will depend on the local patient pathway.

Consent will be obtained either by face to face at a clinic appointment or remotely by telephone/video call or electronically using a purposed designed electronic database. The consent process will be described in detail in the study manual. Participants who consent via video call or telephone will be guided through the process of completing the consent form by the local research team. Participants will be asked to return their signed consent form by:

- scanning or taking a photograph of the form(s) and emailing the form(s)
- posting the form(s) to the research team
- bringing the form(s) to their next hospital visit

On receiving the consent form(s) the research team will check for errors, counter sign and date. Photocopies of the consent form(s) will be made and the research team will ensure that the participant is given a copy of their countersigned consent form(s) at a hospital visit or is sent copies by post or email as preferred. The counter-signed consent form will be retained at the study site, and a copy will be filed in the medical notes. Details of all participants approached for the study and reason(s) for non-participation (e.g. reason for being ineligible or participant refusal) will be documented. Eligibility will be confirmed by a clinician prior to randomisation.

6.10 Discontinuation/withdrawal of participants

Each participant has the right to withdraw at any time. It is unlikely for this trial that there would be any reason for the investigator to withdraw the participant from their allocated treatment, unless subsequent to randomisation, a clinical reason for not performing the surgical procedure is discovered. In the unlikely event that a participant loses capacity during the study they will be withdrawn. Any information already collected about them will be used, and where appropriate the collection of routine data for these patients will continue.

All withdrawals, including reasons (where given), will be recorded. If a participant wishes to withdraw, data collected up until that point will be included in the analyses. Passive data collection (e.g. from medical records) will also continue, unless the participant expresses a wish for this to stop. This is explained in the PIL.

6.11 Frequency and duration of follow up

Follow up will be face-to-face and via questionnaires. Questionnaires will be administered at at approximately 3, 6, 12 and 24 months post randomisation for information on knee function, activity, HRQoL, return to work and resource use.

Participants will attend the site for follow-up at approximately 3 months, 6 months, 1 year (all routine care) and at 2 years (research-specific follow-up). Data will be collected at these visits and with alternative arrangements for participants who do not attend (e.g. postal or on-line data collection, telephone follow-up at mutually agreed times).

All questionnaires will be administered by a research nurse at each participating centre in person, by post or online. Participating centres will be responsible for collecting these from patients and entering them into the study database. Reminders will be sent approximately 2 weeks after the initial contact if no reply has been received. A maximum of 3 reminders will be sent per time point. Participants can opt in to receive text message reminders. The SMS service will be provided by Three Cherries Limited, a third party vendor, contracted by the University of Bristol under a long-standing agreement to provide an SMS for research purposes.

Further follow up may continue for up to 10 years subject to further funding.

6.12 Likely rate of loss to follow-up

Until discharge from hospital, the only losses to follow-up will be due to death, a participant withdrawing or ceasing to engage in follow-up; these losses are expected to be very few. In estimating the target sample size for the study, a loss to follow-up of 20% has been allowed for.

6.13 Expenses

Participant travel expenses will not be reimbursed for the 3, 6 and 12 month follow up visits which are expected to occur as part of normal surgical follow up. Exceptions to these can be considered on a case by case basis. A limited amount of expenses will be available for the 24 month follow up visit which is a research-specific visit that would not be expected to occur as part of normal surgical follow up.

7. Statistical analyses

7.1 Plan of analysis – primary and secondary outcomes

Primary analyses will be by intention-to-treat (ITT) and will be directed by a pre-specified statistical analysis plan. Analyses will use data from all patients randomised. Primary and secondary outcomes will be compared using mixed model (continuous variables measured at multiple time points) regression, or logistic regression (binary variables). Mixed models allow all patients with data to be included in the analysis, i.e. partial missing data (assumed missing at random) is permitted. Interactions between treatment and time will be examined and if significant at the 10% level, results will be reported separately for each postoperative time point; otherwise overall treatment effects will be reported. Model validity will be checked using standard methods; if a model is a poor fit, alternative models or transformations will be explored. Outcomes analysed on a logarithmic scale will be transformed back to the original scale after analysis and results presented as geometric mean ratios. Analyses will be adjusted for baseline values and centre and surgeon will be fitted as a random effect. Findings will be reported as effect sizes with 95% confidence intervals, and in accordance with the CONSORT reporting quidelines.

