This trial was developed in collaboration with the University of Bristol Musculoskeletal Research Unit patient involvement group; the 'Patient Experience Partnership in Research (PEP-R) comprises nine members who have had, or are having, treatment for musculoskeletal health conditions, several of whom have had knee surgery. They suggested that this research was taken to them for their views in a larger group setting, rather than members attending trial management group meetings. They therefore felt that their contribution would be most efficient in the following ways: A) The group should discuss the project 6 times over the 5 year grant, with 2 meetings in the first year. B) At the start of the project, they will discuss study background, research methods, methodology and ethics. C) They will review the information for participants, including invitation letters, information sheet and consent form. D) They will review the questionnaires/outcome measures. E) They will advise on keeping participants engaged, including reviewing newsletters and the summary of results for participants. F) They will monitor the progress and conduct of the study and work with the study team to identify and prioritise next steps. G) At the final meeting, they will discuss how to communicate the results to a lay audience. H) The meetings will be organised and facilitated by an experienced patient and public involvement coordinator, [name] (co-applicant). She will attend the trial management group meetings. The group were happy for her to represent the group and provide feedback to them. She will provide ongoing support and tailored development to PEP-R members and advise researchers on good practice.

4. Aims and objectives

We hypothesise that in patients with symptomatic chondral or osteochondral defects of the knee requiring treatment, microfracture with microstructural scaffold leads to a superior Knee Injury and Osteoarthritis Outcome Score (KOOS) outcome at 2-years compared with microfracture alone. The overall aim of this study is to evaluate the clinical and cost effectiveness of microstructural scaffold in patients undergoing microfracture for a chondral or osteochondral defect of the knee.

Specific objectives of the trial are:

[figure not shown]
- 1. To estimate the difference between groups in mean Knee Injury and Osteoarthritis Outcome Score (KOOS) at 2 years

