5.7 Primary and secondary outcomes

5.7.1 Primary outcome

Following the consensus statement recommendations of the International Cartilage Repair Society Recommendations, (10) the primary outcome is the participant-reported Knee injury and Osteoarthritis Outcome Score (KOOS) which is a validated score for articular cartilage repair 2 years post-randomisation.(11)

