5.8 Sample size calculation

The MCID for the KOOS at 2 years is 10 points(20, 21) and the standard deviation (SD) is approximately 18 in the population of interest.(20, 21) A total sample size of 176 participants (88 per group) will provide 90% power to detect an effect size of 10/18 (=0.56) SD with 5% statistical significance (two-tailed), allowing for up to 20% loss to follow-up.

The sample size calculation has not accounted for the repeated administrations of the KOOS after surgery. Assuming that each participant completes at least two questionnaires over the two years of follow-up (and at baseline) and that there is a moderate correlation of 0.7 between the repeated scores, the study will have 90% power to detect a difference of 0.25 SD in a longitudinal analysis.

6. Trial methods

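### Unless the treatment-by-time interaction reaches the 10% level, section 7.1 reports KOOS as an effect averaged over 3 to 24 months, not the 2-year difference the trial is built to estimate

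*Protocol*

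**What the plan says.** Four places in the protocol set the target at 2 years.

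- Section 4, hypothesis: the scaffold "leads to a superior Knee Injury and Osteoarthritis Outcome Score (KOOS) outcome at 2-years compared with microfracture alone".
- Section 4, objective 1: "To estimate the difference between groups in mean Knee Injury and Osteoarthritis Outcome Score (KOOS) at 2 years".
- Section 5.7.1: the primary outcome is participant-reported KOOS, "which is a validated score for articular cartilage repair 2 years post-randomisation".
- Section 5.8: "The MCID for the KOOS at 2 years is 10 points", and "the standard deviation (SD) is approximately 18 in the population of interest". On that basis, "A total sample size of 176 participants (88 per group) will provide 90% power to detect an effect size of 10/18 (=0.56) SD", at two-sided 5% with 20% loss to follow-up.

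Section 5.8 adds that the repeated KOOS measurements were not used in this calculation. It then states separately that a longitudinal analysis would have 90% power for 0.25 SD, assuming a correlation of 0.7 between scores.

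KOOS is collected at baseline and at 3, 6, 12 and 24 months (section 6.6, Table 1). Section 7.1 analyses continuous outcomes measured repeatedly, primary and secondary alike, with a baseline-adjusted mixed model. After examining the treatment-by-time interaction, the rule is: "if significant at the 10% level, results will be reported separately for each postoperative time point; otherwise overall treatment effects will be reported". Nothing in the protocol exempts KOOS or guarantees a 24-month estimate. Section 7.3 fixes when the primary analysis is done, not which contrast it reports.

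**The concern.** The quantity reported for the primary outcome depends on a preliminary test. When the interaction is not significant, the result is one effect across four visits, and the 3-month visit counts alongside the 24-month visit. Under section 6.3.3, participants spend the first 6 weeks braced with protected weight bearing, so early scores may respond differently from scores at 2 years.

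The trial is sized on a single-time-point difference, not on detecting an interaction. Moderate variation over time can therefore go undetected, and a non-significant test is weak evidence that the effect is constant. Two things are at stake. An early benefit that has faded by 2 years can be reported as a positive primary result. A benefit that grows can be reported as a smaller number and then judged against a 10-point MCID defined at 2 years.

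**Working it through.** **1. The plan's own figure.** With difference 10, SD 18, two-sided 5% and 90% power, the two-sample t-test needs 69.06 per arm, rounded up to 70. Allowing for 20% loss, 70/0.8 = 87.5, rounded up to 88 per arm and 176 in total. The stated figure reproduces, as a comparison at one time point.

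**2. Inputs for the reporting rule.**
- From section 5.8: SD 18 and correlation 0.7 between repeated scores.
- From step 1: 70 evaluable per arm.
- From section 6.6: visits at 3, 6, 12 and 24 months.
- From section 7.1: baseline adjustment and the 10% interaction test.
- Assumed: equal correlation between all visits, the same 0.7 with baseline (0.4 as a sensitivity case), four complete visits per participant, no centre or surgeon variance, and the effect trajectories. The protocol gives no expected time course.

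**3. Standard errors.** The scale factor is (2/70) × 18² = 9.257.
- 24-month contrast: √[9.257 × (1 − 0.7²)] = √(9.257 × 0.51) = 2.17 points.
- Overall effect, which has equal weights under this covariance: the variance factor is (1 + 3 × 0.7)/4 − 0.49 = 0.285, so the SE is √(9.257 × 0.285) = 1.62 points.
- With baseline correlation 0.4: √[9.257 × (1 − 0.16)] = 2.79 and √[9.257 × (0.775 − 0.16)] = 2.39.

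**4. Chance that the interaction is missed.** The 3-df chi-square test at 10% has critical value 6.25. Its noncentrality is Σ(δ − mean δ)² / [9.257 × (1 − 0.7)] = Σ(δ − mean δ)² / 2.777. The correlation with baseline cancels out of this.
- Effects 4, 3, 2, 0: mean 2.25, sum of squares 8.75, noncentrality 3.15; missed in 59%.
- Effects 2, 1, 1, 0: mean 1.0, sum of squares 2, noncentrality 0.72; missed in 83%.
- Effects 4, 6, 8, 10: mean 7.0, sum of squares 20, noncentrality 7.20; missed in 28%.
- Constant effect: missed in 90% by construction.

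**5. The whole rule.** In 400,000 simulated trials per scenario, the 24-month contrast is used if the interaction is significant and the overall effect otherwise. Superiority means z > 1.96 in favour of the scaffold.

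| True effects at 3, 6, 12, 24 months | Superiority, rule | Rule, baseline correlation 0.4 | Superiority, 24-month contrast (correlation 0.7) |
|---|---|---|---|
| 4, 3, 2, 0 | 17% | 10% | 2.5% |
| 2, 1, 1, 0 | 8% | 5% | 2.5% |
| 4, 6, 8, 10 | 99.6% | 93% | 99.6% |

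For 4, 6, 8, 10, the 28% of trials that miss the interaction report an effect targeting 7.0. Over both branches, the reported 95% interval covers the true 2-year difference in about 84% of trials. With baseline correlation 0.4, the 24-month contrast alone declares superiority in about 95%, against 93% for the rule.

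With no effect at any visit, the rule rejects in about 6% of trials (two-sided), against a nominal 5%.

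**The case against.** The strongest defence has four parts.

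- **The rule is pre-specified and a longitudinal effect was foreseen.** Section 5.8 gives power for a longitudinal analysis. This is true, and the fair description is two targets left unreconciled, not an accidental substitution. But section 5.8 does not redefine the primary outcome, and 176 rests on the 2-year difference.
- **If the effect is constant, the average equals the 2-year effect and is more precise.** This is correct, and in that case the rule does not bias the estimate. A non-significant test does not establish that the effect is constant.
- **The harmful time courses are chosen.** They are assumptions, and a milder fade does less damage. Steep divergence is usually detected. In the overall branch, significance needs only 1.96 × 1.62 = 3.2 points, so a reader with the confidence interval would often see an effect well below 10. That softens the consequence, but the superiority claim would still concern a different quantity.
- **The SAP could report the 24-month contrast as well.** It could, without breaching section 7.1. But the protocol states a rule that conflicts with its objective; this is not a detail left open.

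Three stronger readings are tempting and not supported. A reader might infer that no result is primary when the interaction is significant; section 5.7.1 already identifies the 24-month result. A reader might infer that a late benefit would be missed; in the growing-effect case checked, the chance of declaring superiority falls by at most about 2 percentage points. A reader might infer from "if a model is a poor fit, alternative models or transformations will be explored" that KOOS could be reported as a geometric mean ratio; that text is generic to all outcomes, and nothing says KOOS will be logged.

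**Conclusion.** The point stands for the branch in which the interaction is not significant, and it should be corrected before analysis because it governs the headline result. In that branch section 7.1 does not secure the 2-year contrast required by section 4 and section 5.7.1.

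The size depends on the unknown time course. For the assumed fading effects with nothing left at 2 years, false superiority runs from about 5% to 17%, against 2.5%. For the assumed growing effect, the harm is to the estimate and its interval coverage, not to the superiority claim. With no effect at any visit, the inflation is about one percentage point. These figures also rest on equal correlations and complete visits.

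**What to change.** State in section 7.1 that the primary result is always the 24-month treatment contrast in KOOS from the mixed model, with time categorical and the treatment-by-time term retained, tested at two-sided 5% whatever the interaction test shows. Make the interaction test and the overall effect across visits secondary. Say in section 5.8 that the longitudinal power statement refers to that secondary analysis. Apply the same rule to IKDC, which section 5.7.2 also defines at 2 years, and carry the wording into the SAP.

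The cost is wording only; the sample size stays at 176 and no data are added. If the effect really is constant, the 24-month contrast is less precise than the average (SE about 2.2 against 1.6 points). The trial was sized on the 24-month difference: power for 10 points with 70 per arm is 90.4% without baseline adjustment and 99.6% with it at correlation 0.7.
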